2.5.3. Guidelines for stopping the trial early

The number of vascular access thrombosis and access-related serious adverse events per person-year will be analysed using general linear models with Poisson distribution, and mortality will be analysed using Cox regression. When 72 access-related serious adverse events have taken place, an interim safety analysis has sufficient power to show non-inferiority with regards to access-related serious adverse events at a margin of 0.5 events per patient-year with a power of 90%. When non-inferiority has not been reached, further analysis for superiority of either study group will be done. Statistically significant differences between study groups will be used as a guideline to issue recommendations by the DSMB. Reasons to disregard a statistically significant difference between study groups by the DSMB will be recorded. More weight will be given to access-related serious adverse events than to vascular access thrombosis. When the analysis shows neither non-inferiority nor superiority, additional interim safety analyses with more follow-up time may be done at the discretion of the DSMB.

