5.1.2. Secondary outcomes

1. Access-related complications per patient-year

Separate analyses will be performed on access-related complications graded as Clavien-Dindo grade 2 or higher and on access-related complications graded as Clavien-Dindo grade 4 or 5. The outcome will be defined as the number of access-related complications per patient-year.

- Access-related complications of Clavien-Dindo grade 2 or higher will be registered (30). Grade 2 complications require pharmacological treatment including catheter thrombolysis, antibiotics and blood transfusions. Complications that require no pharmaceutical or interventional treatment (grade 1) are not considered relevant for this clinical trial.
- Access-related complication of Clavien-Dindo grade 4 or 5 (i.e. admission to intensive care unit or death) are considered serious adverse events. As an exception, postoperative intensive care unit admission for vasopressor therapy to prevent early vascular access thrombosis is not considered a serious adverse event or complication.

2. Vascular access thrombosis rate

Vascular access thromboses will be defined as the absence of thrill and bruit, with confirmation of no flow by duplex ultrasound if deemed necessary by the treating physician at the study site. The outcome will be defined as the number of vascular access thrombosis events per person-year.

3. All-cause mortality

All-cause mortality will be defined as death by any cause during follow-up.

4. Access-related health care costs from randomization until the end of follow-up

Healthcare costs will be derived from hospital registration systems at the individual participant level. Costs to patients and families will be measured at the individual participants level using a study-specific adaptation of the Medical Consumption Questionnaire and Productivity Cost Questionnaire

developed by the institute for Medical Technology Assessment. Patients will be asked to report the data from their cost questionnaire every 3 months during the follow-up period.

5. Patient-reported outcome measures

For the patient-reported outcome measures the Short-form Vascular Access Questionnaire (SF-VAQ) and the Dutch version of the 5-level EuroQol 5-dimensional questionnaire (EQ-5D-5L) will be used.

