5.2.2. Secondary outcomes

Serious adverse events, access-related complications and vascular access thrombosis:

The number of access-related complications and access-related thromboses for each patient-year of haemodialysis treatment will be analysed using a general linear mixed effect model with Poisson distribution and identity link, and with time as off-set variable. The outcome will be expressed as a ratio (exponential of β_1) of events (number of interventions) per 1 unit increase of exposure time between both groups. A random intercept for each individual participant will be estimated to account for dependence of observations. Expected counts will be plotted against observed counts to check whether the distribution of counts follow a Poisson distribution. Furthermore, the Pearson dispersion statistic will be assessed to check whether there is equidispersion of the variance compared to the mean. In case of overdispersion of the data, a quasi-Poisson model or negative binomial model will be performed. Sensitivity analyses will be done for the primary outcome with major interventions having twice the weight of minor interventions, and with exclusion of patients with access-related interventions with technical failure (residual stenosis $>30\%$) and clinical failure (flow volume $<500\text{mL/min}$ in the first week after intervention and/or failure to restore vascular access function and clinical signs of flow dysfunction).

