5.4.1. Interim analysis

Interim analysis has already been described in section 2.5 and uses the same statistical techniques as described in section 5.2.2.

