Statistical analysis (intention to treat population): general linear mixed effect model with Poisson distribution and identity link, and with time as off-set variable. The outcome will be expressed as a ratio (exponential of β_1) of events (number of interventions) per 1 unit increase of exposure time between both groups. A random intercept for each individual participant will be estimated to account for dependence of observations. Expected counts will be plotted against observed counts to check whether the distribution of counts follow a Poisson distribution. Furthermore, the Pearson dispersion statistic will be assessed to check whether there is equidispersion of the variance compared to the mean. In case of overdispersion of the data, a quasi-Poisson model or negative binomial model will be performed.

Stratification: study site and vascular access type (fistula / graft).

Subgroup analysis: vascular access type (fistula / graft).

Sensitivity analysis:

- Major interventions counting twice (see Table 3a-2)
- Exclusion of patients with interventions with technical failure (see Table 7A)
- Exclusion of patients with interventions with clinical failure (see Table 7A)

Table 3B: Characteristics of vascular access interventions

	Monitoring (N=...)	Surveillance (N=...)	P
Indication			
Clinical indicators of flow dysfunction ^a	%	%	...
Physical examination			
Weak or discontinuous thrill	%	%	...
High pitched or discontinuous bruit	%	%	...
Hyperpulsatile vascular access	%	%	...
Weak vascular access	%	%	...
No thrill or bruit	%	%	...
Recurrent problems during dialysis			
Inability to achieve target blood flow	%	%	...
New cannulation problems	%	%	...
Prolonged bleeding	%	%	...
Unexplained fall in dialysis efficiency	%	%	...
Access flow <500 mL/min without clinical indicators of flow dysfunction ^a	%	%	...
Vascular access thrombosis	%	%	...
New vascular access	%	%	...
Non-maturation	%	%	...
Central venous catheter dysfunction	%	%	...
Unused vascular access	%	%	...
Other than flow dysfunction	%	%	...
High flow	%	%	...
Central vein obstruction	%	%	...
Hand ischemia	%	%	...
Vascular access (pseudo)aneurysm	%	%	...
Vascular access infection	%	%	...
New vascular access	%	%	...
Non-maturation	%	%	...
Central venous catheter dysfunction	%	%	...
Unused vascular access	%	%	...
Anesthesia			...
Local anesthesia	%	%	
Local anesthesia with sedation	%	%	
Locoregional anesthesia	%	%	
Regional anesthesia	%	%	
Hospital admission			...
Outpatient	%	%	
Day case	%	%	

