Extravasation after angioplasty	%	N	%	N	%	N	...
Balloon dilation	%	N	%	N	%	N	
Covered stent	%	N	%	N	%	N	
Other treatment	%	N	%	N	%	N	
Bleeding from access site	%	N	%	N	%	N	...
Compression dressing	%	N	%	N	%	N	
Thrombin injection	%	N	%	N	%	N	
Surgical closure	%	N	%	N	%	N	
Other treatment	%	N	%	N	%	N	
Other complication	%	N	%	N	%	N	...

Statistical analysis: Chi squared tests.

Figure 3E: Patency of vascular access

Kaplan-Meier curves for primary patency (any access-related intervention), assisted primary patency, and secondary patency after randomization. Censoring after loss of primary patency.

Primary patency: interval between randomization and first access-related intervention or thrombosis or access abandonment

Assisted primary patency: interval between randomization and first thrombosis or access abandonment

Secondary patency: interval between randomization and access abandonment

Statistical analysis: Cox proportional hazards regression with a clustered standard error (SE) using a time-to-event framework to account for repeated events in which the same person experiences multiple events over time, some occurring while on the intervention arm, and others occurring while on the control arm. The outcome will be expressed as a hazard ratio (HR) including 95% confidence intervals and p-values. Before running the analyses, we will test the proportional hazards assumption by visual inspection of the log-log survival plots, and the Schoenfeld residuals test to statistically evaluate the assumption.

Table 4A: Serious adverse events

	Monitoring (... patient-years)	Surveillance (...patient-years)	Event rate ratio (95% CI)	P
All serious adverse events	N	N	... (...-...)	...
Related to vascular access	N	N	... (...-...)	...
Unrelated to vascular access	N	N	... (...-...)	...
Vascular access thrombosis	N	N	... (...-...)	...
Vascular access abandonment	N	N	... (...-...)	...
Unplanned hospital admittance	N	N	... (...-...)	...
Related to vascular access	N	N	... (...-...)	...
Unrelated to vascular access	N	N	... (...-...)	...
Death	N	N	... (...-...)	...
Related to vascular access	N	N	... (...-...)	...
Unrelated to vascular access	N	N	... (...-...)	...

Serious adverse events may be included in more than one category.

Statistical analysis (intention to treat population): general linear mixed effect model with Poisson distribution and identity link, and with time as off-set variable (see Table 3A for details).

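### All-cause mortality has no final method of its own: the Table 4A note sends deaths through a repeat-event Poisson mixed model, while the interim analysis uses Cox regression

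*SAP*

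**What the plan says.** - SAP 5.1.2 lists mortality as the third secondary outcome: "All-cause mortality will be defined as death by any cause during follow-up".
- SAP 5.2.2 is headed "Serious adverse events, access-related complications and vascular access thrombosis". Its text models complications and thromboses. It does not name all-cause mortality and contains no Cox model.
- Table 4A has a Death row and two sub-rows (access-related and unrelated) under an event rate ratio column. One note covers the whole table and prescribes a "general linear mixed effect model with Poisson distribution and identity link, and with time as off-set variable (see Table 3A for details". No row is exempted.
- The Table 3A details brought in by that note include a participant effect, "A random intercept for each individual participant will be estimated to account for dependence of observations", and a switching rule, "In case of overdispersion of the data, a quasi-Poisson model or negative binomial model will be performed".
- SAP 2.5.3, on the interim safety analysis, says "mortality will be analysed using Cox regression".
- SAP 5.4.1 says the interim analysis "uses the same statistical techniques as described in section 5.2.2".

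No other between-arm comparison of mortality is planned. Figure 2D compares the survival of enrolled patients with that of an unselected population, and the curves in Figure 3E concern access patency. The SAP states no death rate, hazard ratio or power for mortality.

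**The concern.** The interim and final methods for one outcome differ, and the sentence meant to tie them together points to a section that contains neither a mortality method nor a Cox model. Two analysts could report a Cox hazard ratio, a mixed-model rate ratio, or a quasi-Poisson ratio with a much wider interval, and each could cite the SAP.

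The choice affects the result. A participant intercept is there to absorb correlation between repeated events in one person. With at most one death each, there is no such correlation. Its variance can be estimated only from the way deaths are spread over follow-up, that is, from departures from a constant hazard. The dispersion rule has a related weakness: a death both scores the event and ends the exposure, so early deaths produce very large Pearson residuals even when nobody is frailer than anyone else.

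At stake is the mortality comparison in a trial that asks whether surveillance can be dropped safely. The primary outcome is not affected.

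**Working it through.** **No plan figure to reproduce.** The SAP gives no mortality assumption, so the check is a simulation.

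**Inputs from the SAP:** 417 patients, 1:1 allocation, follow-up of 2 to 3 years.

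**Assumptions:** death rate 0.05 to 0.20 per year when the hazard is constant; cumulative hazard 0.15 × t^shape otherwise; other censoring 0.10 per year; true hazard ratio 1.5 (1.0 in the last row); no between-patient heterogeneity; one record and a fixed arm per participant; 200 trials per row. The mixed model was fitted with a log link, the reading kindest to the SAP, so that the identity link does not confuse the comparison. The Pearson statistic was taken from the Poisson fit without the intercept.

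Median ratios:

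| Hazard | Mean deaths | Cox | Poisson, no intercept | Poisson, random intercept | Trials with intercept model and Cox >10% apart | Median Pearson statistic |
|---|---|---|---|---|---|---|
| Constant 0.05 | 54 | 1.55 | 1.55 | 1.59 | 9% | 5.5 |
| Constant 0.10 | 99 | 1.54 | 1.53 | 1.58 | 6% | 5.9 |
| Constant 0.15 | 138 | 1.50 | 1.50 | 1.53 | 6% | 6.4 |
| Constant 0.20 | 171 | 1.51 | 1.51 | 1.54 | 4% | 6.3 |
| Falling, shape 0.9 | 130 | 1.50 | 1.51 | 1.62 | 28% | 9.0 |
| Falling, shape 0.8 | 122 | 1.56 | 1.58 | 1.80 | 64% | 13.1 |
| Falling, shape 0.6 | 105 | 1.48 | 1.49 | 2.06 | 90% | 32.9 |
| Rising, shape 1.5 | 187 | 1.51 | 1.47 | 1.47 | 0% | 1.9 |
| Falling 0.6, true ratio 1.0 | 87 | 0.98 | 0.99 | 0.99 | 57% | 33.1 |

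**(a) Random intercept.** The model without the intercept tracks Cox in every row, so the offset Poisson model is not the fault. The intercept adds little under a constant or rising hazard. It inflates the ratio when the hazard falls and an effect exists. At a true ratio of 1.0 there is no average bias, though single-trial estimates move.

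At a smaller effect (true ratio 1.3, log 0.262; shape 0.8), mean log ratios were 0.339 to 0.38 with the intercept and 0.256 to 0.28 from Cox. In ratios:
- with the intercept, exp(0.339) = 1.40 to exp(0.38) = 1.46;
- from Cox, exp(0.256) = 1.29 to exp(0.28) = 1.32.

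**(b) Dispersion rule.** The SAP sets no cut-off. The Pearson statistic exceeded 1.2 in every simulated trial, although no heterogeneity was simulated. Under a constant hazard its median was 5.2 to 6.4 across runs. Quasi-Poisson multiplies the standard error by the square root of this value: √5.2 = 2.28 and √6.4 = 2.53.

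Example with 99 deaths split about evenly and an estimated ratio of 1.5:
- standard error of the log ratio ≈ 2/√99 = 0.201; 95% CI 1.5 ÷ and × exp(1.96 × 0.201), or 1.01 to 2.22;
- at dispersion 5.89, 0.201 × 2.43 = 0.488; 95% CI 0.58 to 3.90.

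**The case against.** Several counter-arguments have force.

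- **Interim and final methods may differ.** The Cox sentence is in the stopping section, and Table 4A is a final table. That alone is no contradiction; the conflict arises only through 5.4.1. The one sentence that assigns a method to mortality by name chooses Cox, so a reader might infer that the SAP decided to drop Cox. The text does not support that: a blanket note under a long table looks more like an unstated final method.
- **Death is a serious adverse event, so the 5.2.2 heading may cover it.** If so, 5.2.2 prescribes the Poisson model for death and the mismatch with 2.5.3 becomes sharper.
- **The inflation needs assumptions.** Nothing in the SAP indicates a falling hazard, and excluding patients with a life expectancy under 6 months could point the other way. This stands. A reader might infer that the reported mortality ratio will be biased, or that a false signal of harm will follow. The results under constant and rising hazards and at a ratio of 1.0 do not support either.
- **The two faults need not reach the same number.** If the dispersion rule leads to quasi-Poisson without the intercept, the point estimate is that of plain Poisson, close to Cox, and only the interval suffers. This also stands. The negative binomial option, however, is a Poisson model with a gamma participant effect, so it brings back the problem in (a).
- **Real heterogeneity may exist.** With a simulated log-normal frailty of SD 1, a constant hazard for each patient and a conditional ratio of 1.5, the intercept model gave 1.45 and Cox 1.37. With one death per person, the data cannot separate this case from a common falling hazard, so the intercept model rests on an assumption that cannot be tested here.
- **Repeat allocation.** Figure 2E, Table 2L and the patency method in 5.2.1 show that participants can change groups, so one person may contribute several periods. That may explain the intercept for recurrent outcomes, but it creates no repeated deaths. The simulation does not model switching.

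**Conclusion.** The concern holds as a gap and an inconsistency in method that should be fixed. The final mortality method is left to a table note that carries over two unsuitable rules, and 2.5.3, 5.2.2, 5.4.1 and Table 4A do not agree.

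The size is conditional. The inflation requires both a true effect and a falling hazard. The spurious dispersion signal does not require a falling hazard: it appeared in every scenario and was weakest under a rising hazard. The 2.3- to 2.5-fold wider standard error applies under a constant hazard and only if the quasi-Poisson option is taken. All these figures rest on assumed death rates, hazard shapes and censoring, a log link, and a fixed arm per participant.

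A reader might go further and hold that Poisson regression is wrong for death, or that the trial's main safety conclusion is compromised. Neither follows. The offset Poisson model without the intercept agreed closely with Cox. Mortality is one of several secondary outcomes, and although 2.5.2 includes it in the interim safety review, section 5.5 defines the safety endpoints as access-related events.

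**What to change.** Before unblinding:

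1. In 5.2.2, name Cox regression stratified by study site and access type for all-cause mortality, reported as a hazard ratio with 95% CI.
2. Take the three Death rows out of the Table 3A model. Counts can remain in Table 4A, with a note pointing to 5.2.2 for the comparison. Keep the Poisson model for events that can recur.
3. State whether the arm in the Cox model is the initial allocation or the current allocation as a time-varying covariate. This must be explicit: the baseline tables use initial randomization, Table 2O (which lists deaths) uses allocation at end of study, and Table 4A says only that the population is intention to treat.
4. Reword 5.4.1 so that it points to the same mortality method as 2.5.3.

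The cost is SAP wording. Cox regression is already planned for the interim, and no additional data are needed.

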2.2. Randomization

Patients will be randomized using a 1:1 individual participant treatment allocation ratio. The data management center will generate the treatment allocation sequence by a random number producing algorithm on a computer. Randomization will be stratified by treatment center and for vascular access type (graft vs fistula). The study coordinator will enroll participants and will be informed of treatment assignment through an online service provided by the data management center.

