2.3. Sample size

Sample sizes were estimated for the number of interventions required for each patient-year of dialysis treatment (i.e. the primary outcome), which will be analysed using a general linear model with Poisson distribution and time as off-set variable. In the FLOW project, we aim to detect a difference in the intervention rate of 0.25 per year between study groups in a superiority analysis. This difference is associated with an economically relevant effect of saving approximately 1 million euros per year at a 75% de-implementation rate. The minimal clinically relevant difference in the intervention rate remains to be defined for this core outcome measure, but will likely be greater than 0.25 per year. In the Netherlands, the access-related intervention rate in hemodialysis patients with arteriovenous fistulas and grafts was 1.56 and 3.30 per year, respectively, in a retrospective observation cohort study in 10 dialysis units. As the distribution between fistulas and grafts is approximately 8:1, these figures amount to an average of 1.77 interventions per patient-year in the Netherlands. Since the study includes young hemodialysis patients waiting for kidney transplantation and old hemodialysis patients with limited life expectancy, 20% of participants are expected to leave the study per year before completing the follow-up period. A total follow-up time of 828 patient-years (414 patient-years in each treatment arm) achieves 80% power to detect a 0.25 decrease in the number of interventions per patient-year between the study groups using a two-sided, large-samples z-test of the Poisson event-rate difference at a significance level of 0.05. With a standard follow-up of 2 years and a drop-out rate of 20% per year, this would require a sample size of 518 patients. Implementing a variable follow-up time of a minimum of 2 years and a maximum of 3 years is expected to result in 162 additional patient-years. This corresponds to 101 patients with 2-years of follow-up and a drop-out rate of 20% per year, and therefore leads to a new sample size estimation of 417 patients. An interim analysis for safety requires a sample size of 144 patients (72 in each treatment arm) contributing 1 year of follow-up with an expected event rate of 0.5 events per patient-year to show non-inferiority with regards to access-related serious adverse events at a margin of 0.5 events per patient-year with a power of 90%.

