3.1. General principles

Descriptive analyses will be reported using summary tables and figures. Continuous variables will be summarized with counts, means, standard deviations, medians, confidence intervals, minimums, and maximums where appropriate. Categorical variables will be reported by counts and percentages. Formal inferential statistical analyses techniques will be discussed in subsequent sections of this SAP. P-values <0.05 are considered statistically significant, unless otherwise stated in the SAP. 95% confidence intervals around estimates will be reported, unless otherwise stated in the SAP. Analyses and tabulations will be performed using R. All reported output will undergo a senior level statistical review to ensure valid methods were used, and that all data manipulations and calculations are correct and consistent with the SAP. Upon completion of the analysis, the analyses code will be collected and filed. Missing or invalid data will be treated as missing data (Section 5.3), unless otherwise stated.

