Stratification for study site and vascular access type (fistula / graft).

Subgroup analysis: vascular access type (fistula / graft).

Sensitivity analysis:

- Exclusion of patients with interventions with technical failure (see Table 7A)
- Exclusion of patients with interventions with clinical failure (see Table 7A)

Table 4B: Access-related adverse events

	Monitoring (... patient-years)	Surveillance (...patient-years)	Event rate ratio (95% CI)	P
Access-related adverse events	N	N	... (....)	...
Pain requiring medication (days)	N	N	... (....)	...
Infection requiring antibiotics (days)	N	N	... (....)	...
Bleeding requiring blood transfusion	N	N	... (....)	...
Central venous catheter thrombolysis	N	N	... (....)	...

Statistical analysis (intention to treat population): general linear mixed effect model with Poisson distribution and identity link, and with time as off-set variable (see Table 3A for details).

Table 4C: Hospital admittance

	Monitoring (...patient-years)	Surveillance (...patient-years)	Event rate ratio (95% CI)	P
Hospital admittance (days)	N	N	... (...-...)	...
Related to vascular access	N	N	... (...-...)	...
Unrelated to vascular access	N	N	... (...-...)	...

Statistical analysis (intention to treat population): general linear mixed effect model with Poisson distribution and identity link, and with time as off-set variable (see Table 3A for details).

Table 4D: Line listing of serious adverse events

Table 4E: Line listing of protocol deviations

Table 5A: SF-VAQ scores at baseline

	All patients (N=...)	Monitoring (N=...)	Surveillance (N=...)	P
Total score
Physical domain
Pain
Bleeding
Swelling
Bruising
Social functioning domain
Daily activities
Appearance
Sleep
Bathing and showering
Dialysis complications domain
Problem on dialysis
Access care
Hospitalization
Worry about access longevity

Groups are based on initial randomization

Include only questionnaires with complete data. Questions are Likert scores from 1 to 7. Domain scores are the sum of the 4 questions. The total score is the sum of the 3 domains.

Statistical analysis: Students t-test.

Table 5B: SF-VAQ scores according to the number of interventions during follow-up

	No interventions during follow-up (N=...)	1 intervention during follow-up (N=...)	>1 intervention during follow-up (N=...)	P
Total score
Physical domain
Pain
Bleeding
Swelling
Bruising
Social functioning domain
Daily activities
Appearance
Sleep
Bathing and showering
Dialysis complications domain

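### The fistula/graft subgroup analysis (Tables 3A and 4A) has no test of whether the treatment effect differs by access type, and the two subgroups differ greatly in power

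*SAP*

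**What the plan says.** The notes under the shells of Tables 3A and 4A (SAP section 6) each carry the same line: "Subgroup analysis: vascular access type (fistula / graft". Both also list stratification by study site and access type. The shells give a rate ratio, a 95% CI and a P value for monitoring against surveillance, with no row or column for an interaction. Sections 2.4, 5.2 and 5.4 add no interaction term, heterogeneity test or rule for reading the subgroups. The general rule in section 3.1 is "P-values <0.05 are considered statistically significant, unless otherwise stated in the SAP".

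Section 2.3 supplies the figures that set subgroup precision: "As the distribution between fistulas and grafts is approximately 8:1", and intervention rates for "arteriovenous fistulas and grafts was 1.56 and 3.30 per year, respectively".

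**The concern.** Stratifying by access type adjusts the overall effect. It does not ask whether the effect differs between fistulas and grafts. If the subgroup line is carried out as two separate estimates, each with a P value, the only stated criterion is whether each falls below 0.05. A contrast between one significant and one non-significant result is not evidence of different effects, and here the two subgroups have very different power.

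The trial asks whether surveillance can safely be abandoned. A false contrast could be read as 'monitoring reduces interventions in fistulas but not in grafts', or as a harm confined to one access type, and could then steer practice by access type without support from the data.

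**Working it through.** **Inputs (SAP section 2.3).** 414 patient-years per arm; two-sided 5%; rate difference 0.25 from an average of 1.77, hence 1.52; rates 1.56 (fistula) and 3.30 (graft); split 8:1. Allocation is 1:1 (section 2.2).

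**The plan's own figure.** T per arm = (1.960 + 0.842)² × (1.77 + 1.52) / 0.25² = 413.2, which agrees with the stated 414. Power at 414 is 80.1%. (An exact 8:1 weighting gives (8 × 1.56 + 3.30)/9 = 1.753 rather than 1.77; this moves T by only about 1%.)

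**Subgroup size per arm.** Fistula 414 × 8/9 = 368; graft 414/9 = 46 patient-years.

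**Same rate ratio in both types**, 1.52/1.77 = 0.859, Poisson variance, z = (λ1 − λ2)/√((λ1 + λ2)/T):
- Fistula: (1.56 − 1.340)/√(2.900/368) = 2.48, power 70%.
- Graft: (3.30 − 2.834)/√(6.134/46) = 1.28, power 25%.
- The subgroups are independent, so P(significant in fistulas, not in grafts) = 0.70 × (1 − 0.25) = 53%.

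**Overdispersion.** Sections 5.2.1 and 5.2.2 allow for it but give no value, so a dispersion factor φ of 1 to 3 is assumed, the same in both types. Each z is divided by √φ.

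| φ | Power, fistula | Power, graft | Significant in fistulas only | Overall power |
|---|---|---|---|---|
| 1 | 70% | 25% | 53% | 80% |
| 1.14 | 64% | 22% | 50% | 75% |
| 1.5 | 53% | 18% | 43% | 63% |
| 2 | 42% | 15% | 36% | 51% |
| 3 | 30% | 11% | 27% | 37% |

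**Given a significant overall result.** The unconditional chance falls largely because the whole trial loses power. Subgroup log rate ratios were simulated from normal distributions with the variances above, with an inverse-variance pooled overall test. Among trials with a significant overall result, 'significant in fistulas, not in grafts' occurs in 63%, 64%, 63% and 62% at φ = 1, 1.5, 2 and 3.

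**What an interaction test would do.** Under a common rate ratio, a log-rate interaction test rejects in 5% of simulated Poisson trials. Expected events are 574 and 493 in fistulas and 152 and 130 in grafts, so SE = √(1/574 + 1/493 + 1/152 + 1/130) = 0.134. For 80% power the ratio of rate ratios must be exp(2.802 × 0.134) = 1.46.

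**Serious adverse events (Table 4A).** Section 2.3 expects 0.5 access-related events per patient-year but states no treatment effect and no rate by access type. The chance of 'significant in fistulas only' under Poisson variance is therefore shown over assumed values, with 0.5 per year in fistulas:

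| True ratio | Graft rate 0.5 | Graft rate 1.06 (0.5 × 3.30/1.56) |
|---|---|---|
| 1.1 | 15% | 14% |
| 1.25 | 54% | 49% |
| 1.5 | 66% | 40% |
| 1.75 | 42% | 12% |
| 2.0 | 21% | 2% |

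Using log rates instead moves these by a point or two (67% at ratio 1.5 with equal rates).

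**The case against.** The subgroup line is brief rather than wrong. The shells have no fistula or graft rows, their P column belongs to the overall comparison, and no decision in the SAP depends on subgroup significance. Section 3.1 also requires 95% CIs, so poor precision in grafts would be visible. All of this is true. It makes the side-by-side reading of two P values a likely use of the line rather than a stated rule, but it does not supply a valid comparison.

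A reader might infer three stronger things, none of which the document supports:

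- **That the misleading split is more likely than not, whatever the circumstances.** On the rate-ratio scale that the plan reports, 53% holds only at the full design effect with Poisson variance. It drops below 50% at a dispersion of about 1.14.
- **That the figure is 72%.** That is the result for a common absolute difference of 0.25 (power 81% and 10%). This is not the same effect on the ratio scale: 1.31/1.56 = 0.84 in fistulas against 3.05/3.30 = 0.92 in grafts.
- **That a shared harm would probably show in fistulas only.** A figure near 67% needs a true ratio of 1.5 and equal event rates in both types. The plan gives neither, and other plausible inputs bring it down to 2%.

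Nor is patient-time the whole story: grafts hold one ninth of it but 152/(152 + 574) = 21% of expected control events. Finally, Figure 2E and Table 2L show that participants can be randomized again after an intervention. The parallel-arm arithmetic ignores this, so the figures are approximate.

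**Conclusion.** The concern holds as a gap in the analysis specification. The SAP sets out a fistula/graft subgroup analysis for the primary and safety tables and gives no method for comparing the two effects. For the primary outcome, an identical rate ratio of 0.86 in both types yields 'significant in fistulas, not in grafts' in about 53% of trials under Poisson variance, 36% at dispersion 2 and 27% at 3. Among trials with a significant overall result it is about 62-64% throughout that range. These figures rest on the plan's rates, split and patient-years, on assumed dispersion values equal in both types, and on a simple two-arm comparison. For serious adverse events the chance runs from about 2% to 67% over ratios of 1.1 to 2.0 and the two assumed graft rates, so no single number should be quoted.

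**What to change.** Under Tables 3A and 4A, define the subgroup analysis as a treatment-by-access-type interaction in the stratified count model, on the log-rate scale. The scale must be named: baseline rates differ about twofold between access types, so equal ratios and equal differences cannot both hold, and the SAP currently pairs an identity link with an exponentiated coefficient. Report the ratio of the two rate ratios with 95% CI and P, next to the subgroup rate ratios with their CIs. State that any claim of a different effect by access type rests on the interaction only. Whether the subgroup rate ratios also carry their own P values is a matter of preference.

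The cost is one model term and a few lines of SAP text. The drawback should be written down too: with about 46 graft patient-years per arm, the interaction test reaches 80% power only for a ratio of rate ratios of about 1.46 under Poisson variance, and needs a larger one with overdispersion. A non-significant interaction therefore does not show equal effects.
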